**3. \* Brief description:** 

African Americans were infected and died from SARS-CoV-2 more than any other racial group in United States, including cities such as Flint, MI. Yet, connections to inflammatory biological processes in COVID-19 disparities remains unknown. This study aims to identify and compare inflammation among those with and without confirmed SARS-CoV-2 infection via antibody testing & conduct cross-race comparisons of inflammatory factors. The main objective is to encourage understanding and uptake of antibody testing. The central hypothesis is that African Americans will be receptive to antibody testing when benefits and limitations are communicated in a culturally effective manner. We will provide an opportunity to engage in salivary antibody screening - a non-invasive route to antibody testing that is highly suited to disparities-oriented COVID-19 research.

For the Set-Aside portion of the study: Rural Americans are at greater risk of many COVID-19 outcomes, and these disparities are likely to endure given lower vaccination uptake in many rural communities. Better understanding and addressing these rural disparities could be aided by SARS-CoV-2 antibody testing. However, implementing antibody testing education and outreach is challenged by the racial and regional diversity of rural contexts, as well as skepticism towards COVID-19 testing and treatments in many rural communities. The proposed "set aside" research assembles two disparities-focused SeroNet U01 teams – Michigan State University and the University of Arkansas for Medical Sciences. Together, these teams will adapt and extend their existing SeroNet projects to consider whether video communication for diverse rural populations can effectively encourage understanding and uptake of SARS-CoV-2 antibody testing in rural contexts.

**4. \* What kind of study is this?**

IRB Submission

**5. \* Will an external IRB act as the IRB of record for this study?** 

Yes  No

**7. \* Does the investigator have a financial interest related to this research?** 

Yes  No

**8. \* Is the activity a systematic investigation, including research development, testing and evaluation, designed to develop or contribute to generalizable knowledge?** 

Yes  No

**9. \* Does the activity involve a living individual about whom an investigator (whether professional or student) conducting research obtains data through intervention or interaction with the individual, or identifiable private information?** 

Yes  No

**10. \* Is this project being conducted to fulfill the requirement of an education/training program?**

Yes  No

## Study Scope

**1. \* Does the study specify the use of an approved drug or biologic, use an unapproved drug or biologic, or use a food or dietary supplement to diagnose, cure, treat, or mitigate a disease or condition? **

Yes  No

**2. \* Does the study evaluate the safety or effectiveness of a device or use a humanitarian use device (HUD)?**

Yes  No

## Additional Study Information

**1. \* Describe the research procedures that involve obtaining information or biospecimens about a living person through interaction or intervention and/or by obtaining their identifiable private information or identifiable biospecimens. If subjects will participate in or undergo an intervention, fully describe the intervention. **

Human subjects in the proposed research will be engaged in an experimental study involving exposure to either standard (i.e., generally applicable) or culturally-targeted

informational videos materials about salivary testing for SARS-CoV-2 antibody. These brief videos in conjunction with the survey questions will be distributed via Qualtrics to the Flint community. The Flint Registry will provide contact information and demographics of eligible subjects to the SeroNet team. The SeroNet team will be recruiting participants via email/phone/mail. In collaboration with leading salivary bioscience experts, we will also furnish an opportunity to engage in salivary antibody screening – a non-invasive route to SARS-CoV-2 antibody testing that is highly suited to disparities-oriented COVID-19 research. Video materials will be developed in collaboration with clinical and community advisory committees that are highly suited to the proposed research, and we will present materials as professionally prepared online modules. Participants will also have the option to complete a spit kit in which their collected saliva will be used to enable assays for a dozen salivary cytokines, which we will link to antibody status.

In addition, we will offer an additional opportunity for eligible participants to complete up to 2 more SARS-CoV-2 antibody test kits. Eligible participants are those that have completed a SARS-CoV-2 antibody test kit in our study, have received the COVID-19 booster shot, and are eligible to receive and plan/are scheduled to receive a second COVID-19 booster shot. These qualified participants will be asked to complete a second SARS-CoV-2 antibody test kit before their second COVID-19 booster shot and a third SARS-CoV-2 antibody test kit within 2 weeks after receiving their second COVID-19 booster shot. Participants will receive two additional \$50 electronic gift cards for completing the second and third SARS-CoV-2 antibody test kits. Recruitment will be conducted using the phone, text, and email contact information we have on file for eligible participants. Participants will be asked if they'd like to participate in this opportunity as explained above. Only participants that completed our 'spit kit' consent form will be contacted to complete 2 additional tests. The processes used to complete the additional two antibody test kits will follow the same protocols used for the initial spit kit test. Eligible participants will be contacted via phone/text/email to see if they would like to complete two additional test kits and receive two additional \$50 electronic gift cards for doing so.

## **2. \* Describe the subject population.**

This study will recruit both male and female participants who are Black/African-American or White/Caucasian and enrolled in the Flint Registry. All participants will be 18 and over. We aim to recruit a total sample size of 500 individuals. We will stratify by age and recruit even sample sizes of  $N = 167$  children 18-21, young adults 22-40; and older adults 40 and above (see Inclusion of Individuals Across the Lifespan). Each age group will be further stratified by race and gender. We will recruit a two-thirds African American sample ( $N = 110$ ), and a one-third White sample ( $N = 57$ ), both of which will be one-third to one-half male. The inclusion of both a one-third White sample and a one-third male sub-sample will ensure that we are able to conduct effective race and gender comparisons.

For the vaccination/boosting arm of research, we seek to recruit 200 total male and female participants who are Black/African-American or White/Caucasian. Participants must have received a SARS-CoV-2 vaccination booster within the past 24 hours to be enrolled. We aim to recruit a one-half African American sample ( $N = 100$ ), and a one-half White sample ( $N = 100$ ), both of which will be one-third to one-half male.

For the Set-Aside portion of the study: We will recruit 400 rural participants: 200 each from Arkansas and northern Michigan. Arkansas recruitment will be led by [name]. Arkansas inclusion criteria are resident African American, 18 years and over, and recruited from selected Arkansas rural counties and zip codes. Northern Michigan inclusion criteria are White American, 18 years and over, and recruited from counties considered rural based on the Economic Research Services' rural-urban continuum codes. In both recruitment locations, we will measure but not exclude based on prior SARS-CoV-2 natural infection and vaccination.

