\* Provide details concerning payment, including the amount and schedule of payments including any terms and conditions and who will provide payment (e.g. MSU, another institution). Payment should be proportionate to participation.

We will recruit 500 participants to conduct the proposed research. Each participant will be compensated \$50 for one online session lasting approximately 45-60 minutes. This session will include completing prescreening, viewing educational materials, and filling out an initial immediate outcome survey measure. Participants can be compensated an additional \$50 for completing a salivary assay kit for antibody testing, and for inflammatory profiles.

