**12. \* Will your research likely require non-exempt (expedited or full board) review?** 

Yes  No

**\* (1) Describe the criteria for who will be included or excluded from the study, including how subjects will be screened for eligibility.**

The formal inclusion criteria broadly encompass Flint area community members who are Black/African-American or White/Caucasian, 18 years and above, and enrolled in the Flint Registry. We will exclude participants who do not meet age or race criteria. Although we will not intentionally exclude them, our sample will include individuals from the Flint community who have ready access to interest – the primary mode of enrolling in the Flint Registry.

For the Set-Aside portion of the study: We will recruit 400 rural participants: 200 each from Arkansas and northern Michigan. Arkansas inclusion criteria are resident African American, 18 years and over, and recruited from selected Arkansas rural counties and zip codes. Northern Michigan inclusion criteria are White American, 18 years and over, and recruited from counties considered rural based on the Economic Research Services' rural-urban continuum codes. In both recruitment locations, we will measure but not exclude based on prior SARS-CoV-2 natural infection and vaccination. We will exclude participants who do not meet age or race criteria.

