**Statistical Analysis Plan:**

The primary analysis for all self report study outcomes is based on assessing mean differences across the two study arms. Our arms include rural residents who are assigned either to the general (group 1) or rural targeted (group 2) antibody video group. A series of independent samples t-tests were conducted for all interval level/self-report outcomes, which included Theory of Planned Behavior and rural-adapted anticipatory racism measures. We also computed Cohen's d effect sizes to consider practical significance of pairwise differences. Subsequent analyses will explore sociodemographic variables and individual differences, such as gender and rural identity, as potential moderators of group differences. Future exploratory considerations will utilize hierarchical moderated multiple regression procedures.

For dichotomous (yes-no) outcomes related to accepting and completing the antibody test kit we conducted two group chi square goodness of fit tests.

Please feel free to contact me at [[contact]](mailto:[contact]) with any questions.

Thank you,

[name]  
C.S. Mott Endowed Professor of Public Health  
Charles Stewart Mott Department of Public Health  
College of Human Medicine, Michigan State University

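### Does the 24-hour booster entry rule clash with the repeat-kit offer, and does its absence from the eligibility answer matter?

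*Protocol*

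**What the plan says.** Four places in the Protocol and one in the SAP bear on the point.

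- **Protocol, Additional Study Information, item 1 (procedures).** An extra opportunity is described for people already in the study: "Eligible participants are those that have completed a SARS-CoV-2 antibody test kit in our study". They must also have had one booster and expect another. They are asked to "complete a second SARS-CoV-2 antibody test kit before their second COVID-19 booster shot", and then to do a third kit no later than two weeks after that booster. Only people who signed the saliva-kit consent are contacted. No target number is given.
- **Protocol, item 2 (subject population).** For a vaccination/boosting arm, "we seek to recruit 200 total male and female participants", 100 African American and 100 White. The entry rule is "Participants must have received a SARS-CoV-2 vaccination booster within the past 24 hours to be enrolled". The paragraph gives no booster number, prior kit or kit schedule.
- **Protocol, item 12 (1) (inclusion and exclusion).** Criteria are given for the Flint Registry sample and for the rural Set-Aside sample. Each of the two paragraphs carries the sentence "We will exclude participants who do not meet age or race criteria". The booster arm is not mentioned.
- **Protocol, payment details.** "We will recruit 500 participants to conduct the proposed research".
- **SAP.** "Our arms include rural residents who are assigned either to the general (group 1) or rural targeted (group 2) antibody video group".

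**The concern.** Read quickly, the procedures answer and the population answer seem to describe the same booster work with incompatible timing. One needs a kit before the booster is given; the other admits people only once they have had it. If both applied to the same people and the same booster, someone enrolled under the second rule could not supply the pre-booster kit.

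The eligibility answer then seems to make matters worse. It is where screening criteria belong, and it leaves out both the arm and its 24-hour condition. Staff working from that answer alone would not know of the condition.

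There is also a possible effect on analysis. The brief description sets an aim to "conduct cross-race comparisons of inflammatory factors". The booster arm is split equally by race, while each Flint age group is planned as 110 African American to 57 White. If saliva from the two were merged, recent boosting would be spread unevenly by race through the recruitment targets alone.

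**Working it through.** **Sizes.** These come from Protocol item 2; the totals are sums of its figures.

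- Booster arm: 100 + 100 = 200, which matches the stated 200.
- Flint sample: 110 + 57 = 167 per age group, and 3 × 167 = 501, against 500 stated (rounding).
- Rural Set-Aside: 200 + 200 = 400, which matches.
- All three, if no one is counted twice: 500 + 200 + 400 = 1,100.
- Covered by the eligibility answer: 500 + 400 = 900.
- Remainder: 1,100 − 900 = 200, and 200 / 1,100 = 18.2%.

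The 18.2% depends on there being no overlap. If all 200 came from people already enrolled in the other two components, the number of distinct people would be 900. The documents do not say, so the total lies between 900 and 1,100.

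**The two booster texts side by side.**

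| Attribute | Repeat-kit offer (item 1) | Booster arm (item 2) |
|---|---|---|
| Who | People who have already completed a kit and its consent | People to be recruited; no prior kit required |
| Target number | None | 200, split 100/100 by race |
| Booster status at entry | One received, a second still to come | One received in the previous 24 hours |
| Kit timing | One before and one after the second booster | Not stated |
| How it is described | An added opportunity | An arm with an enrolment rule |

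The texts differ on every attribute that both state, and on how they are framed.

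**Readings.**

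1. *Two components.* The timing rules apply to different people and do not meet. What is missing is a kit schedule and a booster number for the arm.
2. *One component, different boosters.* A person could enrol within a day of a first booster and give a kit before a second. The rules can both be met.
3. *One component, same booster.* The rules conflict, and the passages would have to be reconciled.

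Only reading 3 gives a contradiction, and it needs two assumptions that the text does not make. The table points to reading 1, though that is inference.

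**The eligibility answer.** Its age-and-race exclusion sentence sits inside the Flint paragraph and again inside the Set-Aside paragraph, so it governs those two samples. It gives no criteria for the booster arm, and so no rival rule. The population answer in the same form is the only place from which the arm could be screened, and there the rule is mandatory.

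**Silence elsewhere.** The payment answer counts 500, but it omits the 400 rural participants as well as the arm. The SAP covers rural residents only, so it also omits the 500 Flint participants. Neither silence says anything specific about the booster arm.

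**The case for a change.** The strongest case for acting is that a gap remains on every reading. If there are two components, a 200-person arm has no described kit schedule. If there is one, the text never explains how the timings fit. The omission from the eligibility answer does not depend on the reading at all, and the question there asks expressly how people will be screened. Booster and kit times that were never recorded may be hard to recover, and a cross-race comparison of cytokines could be sensitive to recent boosting. Stating the relation would cost little.

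Much of the factual part stands. The relation is unstated in the available text, the eligibility answer is incomplete, and the arm's procedures are thin.

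The consequences do not stand. Staff could not screen the booster arm from an answer that does not mention it, so they would turn to the paragraph that does. The race imbalance arises only if the arm is merged with the Flint sample, and no passage plans that. A difference in the share of recently boosted people is also not an estimate of bias in any cytokine comparison. The case for date and time fields rests largely on the same unplanned merging. Finally, consent pages and some passages were removed before review, so a schedule missing here may not be missing from the plan.

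**Conclusion.** No change to the plan follows. The available text leaves two details unstated: how the repeat-kit offer relates to the 200-person booster arm, and the arm's entry in the eligibility answer. Both are gaps that a study team would fill sensibly, by applying the mandatory rule where it is written and keeping a differently recruited arm separate in analysis. Following the passages as written leads to no demonstrated wrong result, and the SAP's t-tests and chi-square tests on the rural video groups do not involve this arm.

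The arm is 200 of 1,100 planned participants (18.2%) if components do not overlap. That figure describes the reach of the omission; it does not measure harm. The conclusion rests on reading the two texts as separate components, which their differing terms support but do not prove. Were they one component referring to the same booster, the timing passages would have to be reconciled. No view is taken on which timing rule is right.

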## **3. \* Select the age range (select one).**

Adults who are 18 or older

**4. Identify if your project involves any of the following: (check all that apply)**

**Activities That May Require Additional MSU Reviews:** [?](#)

Biospecimens from humans (e.g. human blood, tissue, cell lines, buccal swab)

**Activities That May Utilize MSU Resources:** [?](#)

There are no items to display

**Activities That May Be Subject To Additional Federal Requirements:** [?](#)

Certificate of Confidentiality

Registration and/or reporting with clinicaltrials.gov (by you or the sponsor)

**Activities That May Be Subject To Additional Requirements Based On Recruitment:** [?](#)

There are no items to display

**Activities That May Be Subject To International Requirements:** [?](#)

There are no items to display

**5. \*** Is this a research study in which one or more human subjects are prospectively assigned to one or more interventions (which may include placebo or other control) to evaluate the effects of the interventions on biomedical or behavioral health-related outcomes? [?](#)

Yes  No

\* Please select one of the options below:

Other

**6. \*** Will any subject's insurance be billed as part of this project? [?](#)

Yes  No

**7. \*** Are you aware of any individual who has a financial interest which may create an organizational conflict of interest? See HRPP policy 10-1, Conflict of Interest, for definitions and additional information. [?](#)

Yes  No

**8. \*** Has any financial arrangement, including compensation, ownership interest, stock options, or other ownership interest, (e.g., compensation that is: explicitly greater for a favorable result; in the form of an equity interest in the sponsor of a covered study; or in the form of compensation tied to sales of the product, such as a royalty interest) been established whereby the value of compensation or ownership interest to investigators conducting the study could be influenced by the outcome of the study?

Yes  No

**9. \*** Do any investigators or research staff have a financial interest related to the research that has not otherwise been disclosed elsewhere in this submission?

Yes  No

**10. \*** Will the research be conducted outside the United States?

Yes  No

**11. \*** Will subjects be compensated for participation in the study (e.g. money, gift cards, coupons for free food)?

Yes  No

\* Provide details concerning payment, including the amount and schedule of payments including any terms and conditions and who will provide payment (e.g. MSU, another institution). Payment should be proportionate to participation.

We will recruit 500 participants to conduct the proposed research. Each participant will be compensated \$50 for one online session lasting approximately 45-60 minutes. This session will include completing prescreening, viewing educational materials, and filling out an initial immediate outcome survey measure. Participants can be compensated an additional \$50 for completing a salivary assay kit for antibody testing, and for inflammatory profiles.

**12. \* Will your research likely require non-exempt (expedited or full board) review?** 

Yes  No

**\* (1) Describe the criteria for who will be included or excluded from the study, including how subjects will be screened for eligibility.**

The formal inclusion criteria broadly encompass Flint area community members who are Black/African-American or White/Caucasian, 18 years and above, and enrolled in the Flint Registry. We will exclude participants who do not meet age or race criteria. Although we will not intentionally exclude them, our sample will include individuals from the Flint community who have ready access to interest – the primary mode of enrolling in the Flint Registry.

For the Set-Aside portion of the study: We will recruit 400 rural participants: 200 each from Arkansas and northern Michigan. Arkansas inclusion criteria are resident African American, 18 years and over, and recruited from selected Arkansas rural counties and zip codes. Northern Michigan inclusion criteria are White American, 18 years and over, and recruited from counties considered rural based on the Economic Research Services' rural-urban continuum codes. In both recruitment locations, we will measure but not exclude based on prior SARS-CoV-2 natural infection and vaccination. We will exclude participants who do not meet age or race criteria.

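### The Set-Aside measures prior infection and vaccination, but the SAP's unadjusted arm comparisons do not use them, which forgoes precision of unknown size

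*Protocol*

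**What the plan says.** The protocol's Set-Aside eligibility text, under item 12 (1) and repeated in item 2 on the subject population, sets the sample: "We will recruit 400 rural participants: 200 each from Arkansas and northern Michigan". Arkansas enrols African American residents and northern Michigan enrols White residents. Of both sites it says "we will measure but not exclude based on prior SARS-CoV-2 natural infection and vaccination".

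The SAP describes two arms, with participants "assigned either to the general (group 1) or rural targeted (group 2) antibody video group". Its main comparison is unadjusted: "The primary analysis for all self report study outcomes is based on assessing mean differences across the two study arms". For scores, "A series of independent samples t-tests were conducted for all interval level/self-report outcomes", with Cohen's d alongside. For accepting and completing the kit, "we conducted two group chi square goodness of fit tests".

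Other variables appear only afterwards, as exploration: "Subsequent analyses will explore sociodemographic variables and individual differences, such as gender and rural identity, as potential moderators of group differences". Hierarchical moderated regression is mentioned as a future step, without a list of terms. The SAP does not mention prior infection or vaccination in any role.

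**The concern.** The plan accepts people whatever their infection or vaccination history, records that history, and then gives it no stated part in the comparison it was collected alongside. The outcomes are attitudes toward, acceptance of and completion of an antibody test. It is plausible that someone's own history bears on whether they want one. The protocol's brief description also brings vaccination into the Set-Aside rationale: "these disparities are likely to endure given lower vaccination uptake in many rural communities".

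If history does predict the outcomes, three things follow. The variation it explains stays in the residual error of the t-tests. A chance difference between arms in the share vaccinated or previously infected is left in the estimate, although a measured variable could remove it. And any later look at the video effect by vaccination status would be chosen after the fact, because it is not named now.

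**Working it through.** **No figure to reproduce.** The documents give no alpha, power, effect size, standard deviation, uptake rate or sample-size calculation for the Set-Aside. Everything below is illustrative.

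**Inputs.** From the protocol: 400 participants, 200 per site. Assumed: 1:1 random allocation (200 per arm), two-sided alpha 0.05, no dropout. Also assumed: the correlation r between the outcome and the two history variables combined. Where site is already in the model, r is the correlation that remains after site.

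**1. Precision for interval outcomes.** Adjustment multiplies the residual variance by 1 − r², so it is worth a factor 1/(1 − r²) in participants. Power at an assumed d = 0.25 is Φ[d / (√(2/200) × √(1 − r²)) − 1.96], where √(2/200) = 0.10.

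| r | 1/(1 − r²) | Equivalent n per arm | Power at d = 0.25 |
|---|---|---|---|
| 0 (unadjusted) | 1.00 | 200 | 70.5% |
| 0.1 | 1.01 | 202 | 71.0% |
| 0.2 | 1.04 | 208 | 72.3% |
| 0.3 | 1.10 | 220 | 74.6% |
| 0.4 | 1.19 | 238 | 77.9% |
| 0.5 | 1.33 | 267 | 82.3% |

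For scale, 200 per arm unadjusted has 80% power at d = (1.96 + 0.84) × 0.10 = 0.28.

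**2. What those correlations require.** For one history variable split 50:50, the gap between history groups in within-group SDs is 2r/√(1 − r²). That is 0.20 at r = 0.1, 0.41 at 0.2, 0.63 at 0.3 and 1.15 at 0.5. The top of the range therefore needs a very large gap.

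**3. Kit acceptance and completion.** Assume uptake near 50%, a 10-point arm difference, and a 50:50 history variable whose groups differ in uptake by g. The unadjusted standard error is √(2 × 0.5 × 0.5/200) = 0.05, so power is Φ(0.10/0.05 − 1.96) = 51.6%. The share of variance explained is 0.25g²/0.25 = g². Power is then Φ[0.10/(0.05 × √(1 − g²)) − 1.96]:

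- g = 0.20: 53.2%
- g = 0.30: 55.4%
- g = 0.40: 58.8%

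**4. Chance imbalance.** The between-arm difference in a binary history variable with prevalence p has standard error √(2p(1 − p)/200). This is 0.046 at p = 0.3 or 0.7, and 0.050 at p = 0.5, so the 95% range is about ±9 to ±10 points. At p = 0.5, an imbalance at that limit moves the uptake difference by 0.098 × 0.20 = 2.0 points to 0.098 × 0.40 = 3.9 points. This movement is random error already counted in the unadjusted standard error. Adjustment would remove it.

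**5. Moderation by vaccination.** With an even split there are four cells of 100. The interaction standard error is √(4/100) = 0.20 SD, and 80% power needs an interaction of 2.80 × 0.20 = 0.56 SD. An uneven split needs more.

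**The case against.** The strongest reply is that nothing is invalid here. Under random allocation the unadjusted tests keep their error rate, chance imbalance is already inside the standard error, and adjusting is an efficiency choice. That stands. A reader might infer that the omission biases the video effect, but the documents do not support that. The SAP says participants were assigned without stating how; if assignment was not random, history could also confound. That is a separate question, and this point does not rest on it.

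A reader might also infer that history is a strong driver of wanting an antibody test. The documents never link a person's history to test intention or uptake. The brief description speaks of community vaccination uptake and skepticism, and its aim concerns diverse rural populations, not the unvaccinated in particular. Nor does the protocol say that history was measured as a substitute for exclusion. The gain could therefore be close to nothing.

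Nor can one say that the effect by vaccination status will go unreported. The SAP's moderator list is given by example, and vaccination history could be added to it. What can be said is that it is not named.

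Two practical objections also stand. Site and race are inseparable in this design and history may differ by site, so any model should contain site, and the gain beyond site is unknown. And the SAP describes its tests in the past tense, so prespecification may no longer be possible. What survives is narrower: the protocol commits to measuring these variables, using them costs little, and the SAP does not do so.

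**Conclusion.** The point holds as a missed, inexpensive gain in precision. It does not show a flaw that invalidates the comparison. Prior infection and vaccination are to be measured at both rural sites, and no stated arm comparison uses them. With random 1:1 allocation and no dropout, adjustment is worth between about 1% (r = 0.1) and 33% (r = 0.5) more participants for an interval outcome. At d = 0.25 that is roughly half a power point to 12 points (82.3 − 70.5 = 11.8). The documents do not say where in that range the trial lies, and the upper end needs large differences between history groups. For the kit outcomes the power gain is about 2 to 7 points, even with assumed uptake gaps of 20 to 40 points.

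**What to change.** In the SAP, add for each self-report score a linear model, and for kit acceptance and kit completion a logistic model reporting a marginal risk difference. Each should contain arm, site, prior infection and vaccination status. Define history as it stood before the video was shown, and give missing self-reports an unknown category. Report the planned unadjusted tests alongside.

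If outcome results have already been seen, say so and label the adjusted models supportive and post hoc.

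Vaccination status may be named among the exploratory moderators, with a note that power for an interaction is low.

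The cost is SAP wording and one extra regression per outcome, with no added enrolment. The protocol already commits to measuring both variables. The documents do not state when history is recorded in the Set-Aside, so the team should confirm that the pre-video status can be established.
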